Other recruitment. Participants will also be recruited from clinic and community flyers, newspaper advertisement, UF HealthStreet, and the UF Pain Research and Intervention Center of Excellence (PRICE), Institute on Aging Pepper Center, and the University of Florida Jacksonville Aging Studies Center Research Participant Recruitment registries.

Screening. All potential participants will undergo an initial phone screening interview, via telephone or in person. We have requested a waiver of written informed consent to retain this information; we will provide verbal consent information and allow participants the chance to ask questions. The initial screening will include questions regarding pain, age, weight, and additional health history information to ensure that no exclusion criteria are present. For participants not affiliated with the University of Florida Health Care system, we will be asking a series of questions to assess any instability of the spine. If instability is determined, the participant must contact their own physician for written permission to partake in the study. If still eligible, participants will be scheduled for an individual in-person baseline assessment during which informed consent will be reviewed, medical and demographic history will be obtained to ensure eligibility, questionnaires will be administered, and a physical performance battery will be conducted to examine lower extremity function. At the completion of the baseline assessment, eligible participants will be scheduled for the intervention program (90 min/session).

Participants. A total of 40 middle-aged and older adults with moderate-to-high impact chronic musculoskeletal pain (e.g., lower back, knee, hip) and overweight/obesity ($BMI \geq 25 \text{ kg/m}^2$) will be targeted. Assuming a 20% attrition rate, an additional 8 subjects will be enrolled, leaving a total of 48 participants to be recruited for study intervention procedures (we anticipate recruiting a total of 60 people to account for screen failures). Participants will still be included if they report the presence of medical pain comorbidities; however, subjects must identify musculoskeletal pain as their primary pain condition.

Inclusion Criteria

- 45-80 years of age
- Have a $BMI \geq 25 \text{ kg/m}^2$
- Endorse pain in the lower back region (i.e., space between the lower posterior margin of the rib cage and the horizontal gluteal fold), knees, or hips

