All participants attending assessments will be required to wear Personal Protective Equipment (PPE) during in-person visits. PPE (masks) will be provided by study staff upon participant arrival or participants may bring their own. In addition, all participants who attend in-person group sessions are required to show proof of COVID-19 vaccination. If proof of COVID-19 vaccination is unavailable, participants will still be eligible to participate through PHI Zoom group sessions. If intervention sessions are conducted through PHI Zoom, study staff will ensure participants have access to Zoom as well as a stable internet connection. Study staff will also ask participants if they have access to a space that will provide confidentiality (e.g., not conducting Zoom call where other people may overhear, inform other household members about confidentiality expectations, ensure no identifying information is visible through camera). Zoom tutorials will be provided during the Baseline Session.

Participants will be compensated \$30 for attending assessment sessions and \$15 per group intervention session. This is comparable to subject remuneration for studies of similar time commitment and invasiveness. Participants will receive partial payment if they do not complete the entire study. For participants traveling more than 25 miles each way to complete in-session study visits, we will reimburse some travel expenses at up to the federal mileage rate (cap of \$200). Payments for participation will occur after completion of each study session and will be handled through the University of Florida's Human Subject Payment Program.

Intervention Procedure. The intervention includes 8 core in-person group sessions and 8 optional in-person group sessions (1.5 hours each) targeting standard weight loss and pain treatment content and eight individual phone calls (30 minutes each) focusing primarily on increasing environmental reward and positive affect. Due to COVID-19, intervention sessions may be delivered online through PHI Zoom. Group sessions will be delivered every-other week and phone

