calls will occur every-other week (during weeks with no group). Sessions will be administered by a study interventionist with bachelors- or masters-level training and certification in health education or a related field (e.g., Certified Health Education Specialist), and materials will be developed to be appropriate for delivery by this level of training, given the potential for greater availability of these types of health professionals. To standardize the application of the intervention and ensure treatment fidelity, the intervention will be manualized and will include interventionist and client workbooks written at the 6th grade reading level.

The standard weight management intervention components are closely adapted from the Diabetes Prevention Program¹⁴ protocol—considered a gold standard weight loss intervention—while the pain coping content is adapted from empirically-supported pain management protocols.^{26, 44, 58} (Table 1). Consistent with standard behavioral weight loss treatments, participants will be assigned a goal of losing 5-7% of baseline weight over the 8-month intervention (with a daily 500 kcal deficit goal) and given recommendations for dietary intake based on the American Heart Association guidelines (e.g., emphasis on whole grains, limitation of saturated fat). They will be asked to engage in daily monitoring of their food and drink intake, either via a free commercial app of their choosing or paper and pen. Physical activity goal setting and monitoring will be integrated in the pleasant activity planning portion of the intervention. To increase non-food environmental reward and positive affect, the first two group sessions will include psychoeducational content addressing the importance of pleasant activities as a way of disrupting the chronic pain and weight cycle, and values clarification techniques to motivate engagement in pleasant activities. At these sessions, participants will also review a list of commonly enjoyed pleasant activities and brainstorm additional activities to include on the list.

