Specific Aim 1: Evaluate the acceptability of the EMPOWER intervention, as indicated by treatment engagement and participant reported treatment credibility and satisfaction, and potential for treatment efficacy. We will examine treatment engagement at each session and will measure

Table 2. Study Measures

Variable	Measure	Time-Point (Month)		
		0	4	8
Participant Engagement	Treatment Engagement Ques.	Every session		
Treatment Credibility	Credibility/Expectancy Scale	X		
Treatment Satisfaction	CSQ-8		X	X
Qualitative Evaluation	Qualitative Interview			X
Pain Impact	RTF Impact Stratification	X	X	X
Body Weight	By Digital Scale	X	X	X
Intensity, Interference, Phys. Function	PROMIS Pain Measures	X	X	X
Functional Performance	BPS	X		X
Back-Related Disability	RMDQ	X	X	X
Physical Activity	IPAQ	X	X	X
Pleasant Activity Engagement	Self-Reported Engagement	X	X	X
Reward from Activities	MAPA	X	X	X
Positive Affect	PANAS	X	X	X
EMA of Pain Intensity	Smartwatch Ratings	X		X
EMA of Mood and Physical Activity	Smartwatch Ratings	X		X
Quality of Life	WHOQol Bref	X	X	X

Note: Ques=Questionnaire; Phys=Physical. See text for a full description of abbreviations for study questionnaires.

several aspects of global acceptability at baseline and at the 4- (mid-intervention) and 8-month (end of intervention) assessment period.

Session-level Engagement. Treatment engagement will assess participants' effort exerted during group activities/phone calls (using a 9-point Likert rating scale), completion of homework (yes/no), and engagement in group and individual discussions (using a 9-point Likert rating scale). Responses will be examined after sessions and after all four cohorts are complete (considering the mean and range of Likert ratings for each questionnaire item). We will also develop a 95% CI around the Likert ratings and examine if our metric for success falls within that interval (i.e., ≥ 6 on a 9-point Likert scale).

Global Treatment Engagement. The mean portion of group and phone sessions attended will be examined across the entire sample, as well as trends in the portion of sessions attended across the four cohorts. We will determine if our metric for success falls within a 95% CI around our identified threshold for success. The percentage of participants who complete $\geq 80\%$ of group and phone sessions combined will also be measured, as well as the portion who complete $\geq 70\%$ of group sessions and $\geq 70\%$ of phone sessions (considered separately).

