Global Treatment Satisfaction and Credibility. On the Client Satisfaction Questionnaire-8 (CSQ-8) and on the adapted Treatment Credibility and Expectancy Scale, we will present the mean (sd) and range as well as develop a 95% CI around questionnaire ratings to examine in relation to our metric for success (i.e., treatment satisfaction: ≥ 3 on a 4-point Likert scale; treatment credibility: ≥ 7 on a 11-point Likert scale).

Potential for Efficacy. To evaluate the potential for intervention efficacy on pain impact, weight, and key putative mediators, we will determine the mean, standard deviation, and range associated with treatment-related changes in these outcomes. We will also develop 95% CIs around the observed mean and examine whether a pre-determined minimal change score is within these CIs. For pain impact, the minimally important change score will be 30% of the baseline score as this number has been previously defined as a clinically meaningful reduction in pain.¹⁹ For weight, the minimal important change score is a 5% reduction in body weight, given that this value is well-established to result in clinically important changes in health parameters.³¹

Specific Aim 2: Determine trial feasibility, including the ability to meet pre-specified recruitment and retention metrics.

Recruitment. We will present the rate of recruitment in units of participants/week (only including weeks of active recruitment). We will also report the portion of participants contacted and screened, including those who were enrolled and reasons for ineligibility. We will develop 95% CIs around the recruitment rate and determine if our metric for success is within that confidence interval (i.e., ≥ 2.5 participants enrolled per week during active recruitment; $\geq 90\%$ of those who enroll commence treatment).

Retention. We will present the portion of participants who attend the 4- and 8-month assessment sessions, by cohort and the total sample. We will determine if our metric for successful retention ($\geq 80\%$ who enroll complete the 8-month assessment, among the final two cohorts) falls within a 95% CI of our obtained retention.

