Data and Safety Monitoring. The proposed trial presents minimal risk to participants. The study PIs, Drs. [name] and [name], will be responsible for data and safety monitoring with oversight from an external Safety Officer, [name] (Duke University). [name] will review the study protocol, Manual of Procedures, and Data and Safety Monitoring Plan prior to enrolling

patients, and will be provided data on certain safety issues that arise during the study and given a summary of all adverse events and at a meeting one year after the start of enrollment. At each in-person group session and assessment period, we will inquire whether any adverse events or unanticipated problems occurred. Additionally, if participants disclose adverse events or unanticipated problems between group sessions (e.g., during phone sessions) they will be systematically recorded on the “Adverse Event and Unanticipated Problems form” developed by the University of Florida’s Institutional Review Board. All serious and unexpected adverse events will be reported to the University of Florida IRB (within 5 working days), the Safety Officer, and the study’s sponsor. Other types of adverse events will be monitored and reported to the University of Florida IRB in the study’s annual progress review. Any adverse events or unanticipated problems reported will be followed until resolution, stabilization, or until it is determined that the study participation is not the cause. The study investigators will review reported adverse events every three months to minimize the risk to study subjects. The principal investigators, Drs. [name] and [name], will be responsible for the timely execution of this plan.

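### Adverse events are actively asked about only at group sessions and assessments, so people who skip groups or leave may not be asked: a minor safety gap that is cheap to close

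*Combined protocol and SAP*

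**What the plan says.** Section 6, Data and Safety Monitoring, sets two ways of finding adverse events. The first is active: "At each in-person group session and assessment period, we will inquire whether any adverse events or unanticipated problems occurred". The second depends on the participant: "if participants disclose adverse events or unanticipated problems between group sessions (e.g., during phone sessions) they will be systematically recorded". Events already reported are followed up, the investigators review reported events every three months, serious and unexpected events go to the IRB, the Safety Officer and the sponsor, and the Safety Officer is "given a summary of all adverse events and at a meeting one year after the start of enrollment".

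Section 6, Intervention Procedure, schedules 8 core groups, 8 optional groups and "eight individual phone calls (30 minutes each) focusing primarily on increasing environmental reward and positive affect". Groups are fortnightly and calls fall in the weeks between them. Groups may be held on Zoom. Under Anthropometric and Medical History, health status is also checked at each group session.

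People who attend only the core groups are still invited to the 8-month assessment (Treatment Outcome and Mediator Measures). Section 7 lets participants stop at any time and acknowledges a slightly raised chance of musculoskeletal injury from the activity component. Neither section describes a safety contact with someone who stops and then does not attend the assessments.

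**The concern.** How completely harm is found depends on attendance. A participant who drops the groups but keeps taking calls speaks to study staff without being asked about adverse events. One who stops sessions and misses both later visits is not asked again under the supplied text.

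Participants are enrolled for back, knee or hip pain, and each is asked to choose an activity goal of at least moderate exertion. Some may stop because of pain or injury. That is an assumption, since the documents give no reasons for stopping, but if it is so, the people most likely to have been harmed are asked least. A count of recorded events would then be too low by an unknown amount. The abstract says the study is to guide a larger randomised trial, whose safety planning would draw on that count.

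**Working it through.** **Where the question is asked.** Setting the sections side by side:

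| Contact | Number planned | Adverse-event question |
|---|---|---|
| Core groups | 8 | Asked |
| Optional groups | 8 | Asked |
| Phone calls | 8 | Recorded only if disclosed |
| Assessments (0, 4, 8 months) | 3 | Asked, if attended |
| After stopping and missing visits | None described | None described |

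The question covers any event that has occurred, and groups are two weeks apart. Someone who attends groups can therefore report a call-week event at the next one; for that person an unasked call mainly delays capture. Someone who skips groups but takes calls is next asked at the 4- or 8-month visit. Someone who also misses those visits is not asked.

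**The plan's own enrolment figure.** Section 6, Participants: "Assuming a 20% attrition rate, an additional 8 subjects will be enrolled, leaving a total of 48 participants".
- 40 × 0.20 = 8, and 40 + 8 = 48. Reproduced.

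**Upper bound on leavers who are not asked again.**
- From the top-up: 8/48 = 16.7%.
- Applying 20% to those enrolled: 0.20 × 48 = 9.6, about 10, and 10/48 = 20.8%.

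**Why this is only a ceiling.**
- The plan does not define its 20% attrition, and the retention metric concerns month 8 only. A person lost at month 8 may have attended groups or the 4-month visit and been asked up to then.
- The recruitment metric accepts 90% of enrollees starting treatment, so up to 0.10 × 48 = 4.8 might never start. If they count as attrition, treated leavers fall to 8 − 4.8 = 3.2, or 9.6 − 4.8 = 4.8.
- If half of the 8 to 10 attend an assessment (an assumption), 4 to 5 of 48 remain (8.3% to 10.4%).

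The number who skip groups but take calls cannot be estimated from the documents.

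**Could events be missed?** No event rate is given. Assume a risk p per person and take 8 people never asked, none of whom discloses. The chance of at least one unrecorded case is 1 − (1 − p)^8:
- p = 5%: 34%
- p = 10%: 57%
- p = 20%: 83%
- p = 30%: 94%

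These are worst-case illustrations, not predictions.

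**Timing of the Safety Officer summary.** At the target of 2.5 enrolled per week, 48/2.5 = 19.2 weeks. Eight months is about 35 weeks. The last participant reaches month 8 at about 19 + 35 = 54 weeks, before any recruitment pause or delay in starting a cohort. A count through month 8 may therefore be incomplete at the one-year meeting.

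**The case against.** The strongest reply is that no planned result depends on this. The aims are acceptability and feasibility in a single-arm study described as minimal risk. No adverse-event measure is among the success metrics, and no harm proportion is calculated. That stands in full: this is not an analysis error.

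Second, the Manual of Procedures and the Data and Safety Monitoring Plan are named but not supplied, and rules for contacting leavers could well sit there. That also stands; the gap is shown only for the supplied text.

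Third, calls are not silent on health. They work through obstacles to meeting activity goals, so an injury may well come up, and disclosed events are recorded. This reduces the gap but does not replace a direct question.

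Fourth, the plan already reports attendance: "The mean portion of group and phone sessions attended will be examined across the entire sample", and "We will present the portion of participants who attend the 4- and 8-month assessment sessions, by cohort and the total sample". The number asked at each assessment can largely be recovered from that. What is lacking is that number placed beside the event count, and any enquiry of those who did not attend.

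A reader might infer three stronger things. One is that half of the core-phase contacts (8 of 16) lose events. They do not for people who attend groups, because the next group asks. Another is that 8 to 10 people will go unasked. That is a ceiling, since it requires both later visits to be missed. The third is that Zoom groups are left out because the sentence says in-person. Zoom is an allowed delivery mode and health status is checked at every group, so this is better treated as wording to tidy.

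**Conclusion.** The point holds as a minor safety improvement. On the supplied text, active enquiry is limited to groups and assessments, and no contact is described for someone who leaves and misses the 4- and 8-month visits. The leavers affected are at most about 8 to 10 of 48 (16.7% to 20.8%), probably fewer, plus an unknown number who take calls but skip groups and wait until an assessment to be asked. How many events this would hide is not known.

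The bound rests on the plan's attrition assumption. The conclusion also rests on the two unsupplied safety documents not already covering leavers; if they do, a single cross-reference in the protocol would settle that part. The gain is more complete safety information to carry into the larger trial.

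**What to change.** In section 6, Data and Safety Monitoring:

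1. Ask the same adverse-event question at every group session (in person or Zoom), every phone session and every assessment. Calls already open with standard questions about goals, so this adds one item.
2. When a participant stops sessions, or misses a 4- or 8-month visit, attempt one brief contact, with the participant's agreement, asking about adverse events and the reason for stopping.
3. In the final adverse-event report, give the number of treated participants asked at each time point beside the number with events, so that people asked with nothing to report are separated from people not asked. Give the same figures to date in the one-year Safety Officer summary.

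Cost: up to 8 × 48 = 384 short extra questions; about 8 contact attempts (8 leavers, one each) to 30 (10 leavers, each triggering all three occasions); and one added column in a report. More minor events will be recorded, each needing a form and follow-up. Sample size, endpoints, eligibility and success metrics are unchanged.

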5. **Hypotheses and Specific Aims:** The central objective of research is to examine the feasibility and acceptability of an 8-month (4-month if only 8 core intervention sessions are completed) single-arm behavioral intervention (i.e., EMPOWER) among overweight/obese middle-aged and older adults with moderate-to-high impact musculoskeletal pain. Intervention content will focus on standard behavioral weight loss treatment and standard cognitive-behavioral pain coping therapy, which will be delivered in a fully integrated manner to take advantage of overlapping techniques used in each (e.g., addressing negative cognitions related to weight and pain in a single session).

Specific Aim 1: Evaluate the acceptability of the EMPOWER intervention, as indicated by treatment engagement and participant reported treatment credibility and satisfaction, and potential for treatment efficacy.

Specific Aim 2: Determine trial feasibility, including the ability to meet pre-specified recruitment and retention metrics.

6. **Research Plan:**

Recruitment

Institutional Data Repository (IDR) Invitational Messages. We will have an IDR search performed for patients who (1) have had appointments in the UF health care system over the last month, (2) have agreed to be contacted for future research (“Consent2share” patients), (3) have a diagnosis consistent with musculoskeletal pain, (4) have a BMI from the past 2 years over 24 kg/m², and (5) are age 45-80. We will obtain a list of patients’ names, email addresses, and mailing addresses. We will also obtain patient sex and race to inform our goals of recruiting a diverse sample. We will send these patients one mailed letter and one email informing them of the study and invite them to share their contact information through a REDCap link provided. In addition to the letter from the study team, the mailing will include a study flyer and a return postcard that patients can mail to study investigators if interested in participation. The email and letter will include a link to a video to learn more about the study. Patients who share their contact information will then be called by study staff to complete the phone screening.

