Electronic data from the smartwatches will be stored on password protected, secure and encrypted Amazon AWS servers according to UF policy. The collected data includes raw accelerometer data (acceleration values in three x, y, and z direction and timestamp), heart rate (per minute), GPS readings (latitude, longitude), mood, pain, activity type, and timestamps. The smartwatch does not collect restricted data – it does not collect health information and it is not connected to identifiable information. Therefore, the data collected on the device is exempt from encryption standards set forth by the UF Information Security Policies and Standards. All devices will be clearly marked as not for use with restricted data and will have a durable physical or electronic label with contact information sufficient to facilitate an expedient return to study staff if a lost device is found. Each device is coded with a number that is assigned to a participant. This assignment document is housed under a secure local server per UF Information Technology Security Charter and managed by the study staff. Data from the smart-watch is temporarily stored, remotely sent to secure servers and then erased from the local disc. Therefore, data on the smartwatch is “not” stored locally — it is permanently erased after uploading it to the Amazon AWS server. Data sent to the server is protected in locked and secure lab with strong password protection and full disk encryption.

Confidentiality. All trained personnel assisting with the study will be instructed on the importance of protecting participants’ confidentiality and will have successfully completed the required education on protection of human research participants. All paper and computer records will be identified only by subject number rather than by name. All study records will be stored in locked file cabinets and will only be available to the PI or other project staff. Computer data files (without subject identifiers) will be stored on computer servers with secure passwords and electronic storage devices will be encrypted. All study records will be stored in locked file cabinets and will only be available to the PI or other project staff. Study staff will be instructed to not record any information (e.g., responses to pain criteria) obtained during the phone screen.

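### The protocol both plans to retain and forbids recording phone-screen information, so reasons for ineligibility promised under Aim 2 may have no source for people excluded by phone

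*Combined protocol and SAP*

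**What the plan says.** Three parts of the protocol bear on this.

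- **Research Plan, Screening.** Everyone is screened first: "All potential participants will undergo an initial phone screening interview, via telephone or in person". On content: "The initial screening will include questions regarding pain, age, weight, and additional health history information to ensure that no exclusion criteria are present". On keeping the answers: "We have requested a waiver of written informed consent to retain this information", with consent information given verbally. On what follows: "If still eligible, participants will be scheduled for an individual in-person baseline assessment during which informed consent will be reviewed".
- **Confidentiality.** The last sentence of the paragraph reads: "Study staff will be instructed to not record any information (e.g., responses to pain criteria) obtained during the phone screen". It makes no exception for a reason code, an anonymous tally, or people found ineligible.
- **Statistical Methods, Specific Aim 2, Recruitment.** The planned report is: "We will also report the portion of participants contacted and screened, including those who were enrolled and reasons for ineligibility".

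The repository-based recruitment text adds that "Patients who share their contact information will then be called by study staff to complete the phone screening". The repository lists supply contact details, provider name (for the provider-letter route), sex or gender, and race. Age, BMI and diagnosis serve as search filters.

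**The concern.** One section plans to retain the initial-screen information and another forbids recording any of it from the phone screen. Both are current text, and a coordinator cannot follow both.

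The conflict matters because Aim 2 is about feasibility, and the abstract says the pilot is to guide a larger randomised trial. Knowing which criteria turn people away helps set that trial's eligibility rules and recruitment plan. If the Confidentiality rule is the one applied, the report cannot say why people failed on what is asked by phone: pain, age, weight and health history. A reason not written down at the call is lost for good.

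**Working it through.** No sample size, power or error-rate figure enters this point. The check sets the passages side by side and traces where a reason for ineligibility could come from.

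**Step 1: can both instructions hold?** Screening seeks permission to retain the information. Confidentiality bars recording any information from the phone screen. Retention requires a record, so they cannot both be followed as written. The waiver is described only as requested; the documents do not say whether it was granted.

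**Step 2: sources of a reason, if the Confidentiality rule governs.**

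| Where the person drops out | Possible source | Reason available? |
|---|---|---|
| Phone screen | Screen record (forbidden); baseline visit (not reached); repository list (no screening answers) | No |
| Initial screen held in person | Screen record, if the rule covers telephone calls only | Yes on that reading |
| Study physician's record review | Review outcome | Yes |
| Baseline visit | Medical history, cognitive test, blood pressure, measured height and weight | Yes |

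The second row is uncertain. Screening calls the interview a phone screening even when it is held in person, so the rule could also reach some in-person screens.

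**Step 3: sources if the Screening text governs and the waiver is granted.** The reasons are available and Aim 2 can be reported as promised. However, the Possible Discomforts and Risks section relies on the Confidentiality steps to lower privacy risk. Keeping the answers while that sentence stands would make one stated safeguard untrue. One passage has to change in either case.

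**Step 4: which Aim 2 quantities use phone-screen answers?**

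1. At least 2.5 enrolled per week of active recruitment: uses enrolments and weeks. Not affected.
2. At least 90% of enrolled participants start treatment: uses enrolled participants. Not affected.
3. At least 80% of enrolled participants in the final two cohorts complete the 8-month assessment: uses enrolled participants. Not affected.

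Numeric criteria affected: 0 of 3. Counts contacted and screened can still be kept, because a tally of calls is not information obtained during the screen. The one output affected is the list of reasons for ineligibility.

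**Step 5: how many people?** The Participants section plans 48 for the intervention (40 × 1.20 = 48) and 60 recruited to allow for screen failures, so 60 − 48 = 12 anticipated failures, or 12/60 = 20%. The protocol does not say at what stage those 12 fail, or whether the 60 includes people excluded by phone. It gives no count of people phone-screened and no split between telephone and in-person screens. The number without a recorded reason therefore cannot be calculated.

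**The case against.** The strongest reply is that the harm sits on the less likely branch. The Screening section describes the actual procedure and gives the purpose of the waiver, and the Aim 2 report needs the retained reasons. The opposing sentence closes a general confidentiality paragraph that also repeats its statement about locked cabinets, which suggests text carried over without editing. Screening also requires people from outside the health system with suspected spinal instability to obtain written permission from their own physician, which is hard to manage if nothing is noted. This is a fair guess at what was intended. It does not tell staff which instruction to follow, and the documents do not settle it.

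Softer readings are possible. The prohibition might be a default until the waiver is granted, might bar individual answers but allow an unlinked tally of categories, or might be refined in the Manual of Procedures, which is named but not available here. None of these is stated. The wording covers any information, and its own example, answers to the pain criteria, is the kind of answer that decides eligibility.

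It can also be said that little is lost: a partial gap in one descriptive item without a success threshold. That stands, and it limits the size of the point. No estimate, confidence interval or progression decision changes.

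**Conclusion.** The concern holds. The two sections contradict each other, and following the Confidentiality rule as written would permanently remove part of an output promised under Aim 2. This should be fixed, but it does not threaten the trial.

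The conflict itself rests on the text alone. The consequence is conditional on the Confidentiality sentence being the one applied, on no exception existing in a document not seen here, and on no other source for the answers of people excluded by phone; the protocol names none. Under those conditions no one excluded by phone would have a recorded reason. If the waiver was granted and the Screening text is followed, the reasons are available and only the wording needs correcting.

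**What to change.** State in the Screening section whether the waiver was granted, and replace the Confidentiality sentence with wording such as:

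> Individual phone-screen responses will be kept only as the waiver allows. Staff will keep a de-identified screening log for each person contacted (date, recruitment source, screened yes/no, eligible yes/no, coded criterion failed), which is the source for the Aim 2 recruitment report.

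The essential fields are screened, eligible and the coded criterion failed. Date and recruitment source are useful but optional, since Aim 2 does not promise them.

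If the coded log is not permitted, amend the Aim 2 Recruitment paragraph to say that reasons for ineligibility are reported only for people excluded other than by phone.

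The cost is two sentences in the protocol, a log template and a check of the waiver's status. The downside is small: a minimal amount of de-identified screening data would be stored.
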